13.4. Reporting Adverse Events

The Investigator will notify the Sponsor of an adverse event by e-mail, facsimile, or telephone as soon as possible and no later than 24 hours from discovery for any serious /significant adverse events, and 2 days from discovery for any non-significant adverse event. In addition, a written report will be submitted by the Principal Investigator to the IEC/IRB according to their

requirements (Section 13.4.2). The report will comment whether the adverse event was considered to be related to the test article, study treatment or study procedures.

13.4.1. Reporting Adverse Events to Sponsor

Serious/Significant Adverse Events

The Investigator will inform the sponsor of all serious/significant adverse events occurring during the study period as soon as possible by e-mail, fax, or telephone, but no later than 24 hours following discovery of the event. The Investigator is obligated to pursue and obtain information requested by the Sponsor in addition to that information reported on the eCRF. All subjects experiencing a serious/significant adverse event must be followed up and all outcomes must be reported.

When medically necessary, the Investigator may break the randomization code to determine the identity of the treatment that the subject received. The Sponsor and study monitor should be notified prior to unmasking the test articles.

In the event of a serious/significant adverse event, the Investigator must:

- Notify the Sponsor immediately
- Obtain and maintain in the subject's records all pertinent medical information and medical judgment for colleagues who assisted in the treatment and follow-up of the subject
- Provide the Sponsor with a complete case history which includes a statement as to whether the event was or was not related to the use of the test article
- Notify the IEC/IRB as required by the IEC/IRB reporting procedure according to national regulations

Unanticipated (Serious) Adverse Device Effect (UADE)

In the event of an Unanticipated (Serious) Adverse Device Effect (UADE), the Investigator will submit a report of the UADE to the Sponsor and IEC/IRB as soon as possible, but no later than 24 hours after the Investigator first learns of the effect. This report is in addition to the immediate notification mentioned above.

The Sponsor must conduct an evaluation of the UADE and must report the results of the evaluation to FDA, the IEC/IRB and participating Investigators within 10 working days after the Sponsor first receives notification of the effect.

Non-Serious Adverse Events

All non-serious adverse events, including non-serious adverse device effects, will be reported to the sponsor by the Investigator no later than 2 days from discovery.

13.4.2. Reporting Adverse Events to the Responsible IEC/IRB and Health Authorities

Adverse events that meet the IEC/IRB requirements for reporting must be reported within the IEC/IRB's written guidelines. Each clinical site will refer to and follow any guidelines set forth by their Approving IEC/IRB. Each clinical site will refer to and follow any guidelines set forth by their local governing Health Authorities.

The Sponsor will report applicable Adverse Events to the local health authorities according the written guidelines, including reporting timelines.

13.5. Event of Special Interest

None

13.6. Reporting of Pregnancy

Subjects reporting pregnancy (by self-report) during the study will be discontinued after the event is recorded as an Adverse Event. Once discontinued, pregnant participants and their fetuses will not be monitored for study related purposes. At the Investigator's discretion, the study participant may be followed by the Investigator through delivery. However, this data will not be collected as part of the clinical study database. Pregnant participants are not discontinued from contact lens or solution related studies for safety concerns, but due to general concerns relating to pregnancy and contact lens use. Specifically, pregnant women are discontinued due to fluctuations in refractive error and/or visual acuity that occur secondary to systemic hormonal changes, and not due to unforeseen health risks to the mother or fetus.

14. STATISTICAL METHODS

14.1. General Considerations

Statistical Analysis will be undertaken by the sponsor or under the authority of the sponsor. A general description of the statistical methods to be implemented in this clinical trial is outlined below. A stand-alone Statistical Analysis Plan (SAP) with more details will be finalized before the interim analysis is undertaken.

All data summaries and statistical analyses will be performed using the SAS software Version 9.4 or higher (SAS Institute, Cary, NC). Throughout the analysis of data, the results for each subject/eye will be used when available for summarization and statistical analysis. Unscheduled visits will be summarized separately and will be excluded from the statistical analysis.

Summary tables (descriptive statistics and/or frequency tables) will be provided for all baseline variables, efficacy variables and safety variables as appropriate. Continuous variables will be summarized with descriptive statistics (n, mean, standard deviation [SD], median, minimum and maximum). Frequency count and percentage of subjects or eyes within each category will be provided for categorical data.

14.2. Sample Size Justification

An adaptive sample size approach is used to allow for modifications based on interim results, with a maximum of 250 evaluable subjects and a minimum of 150 subjects. The enrollment of subjects will be conducted in two phases. In the first phase, up to 160 subjects will be initially enrolled with a target completion of 150 subjects. An interim analysis will take place after initial enrolled subjects have completed the study. This interim analysis will be used for an early claim of success (i.e. demonstrate non-inferiority). If needed, additional subjects will be added to the study, in phase 2, up to a maximum of 260 (see Interim Analysis Section for more details).

The initial sample size of 150 considered in phase 1 was based on historical data from 6 double masked randomized bilateral multi-site studies with the 1 Day ACUVUE MOIST. The table below summarizes the primary endpoints data these studies.

Table 5: 1-week CLUE comfort and vision for 1 Day ACUVUE MOIST in historical studies

	CLUE Comfort			CLUE Vision		
	N	Mean	STD	N	Mean	STD
CR-5777	66	56.38	24.655	66	65.04	22.824
CR-5778	68	63.87	24.693	68	65.17	22.110
CR-5800	138	58.72	22.643	138	61.24	20.643
CR-5801	142	57.21	21.341	142	61.71	19.345
CR-5870	142	60.10	26.356	142	63.52	23.652
CR-5991	70	72.05	21.487	70	72.81	20.624
Total	626	60.49	23.93	626	63.99	21.67

There are no historical data available on how the Test lens will perform against the Control lens. Here we assume no difference between Test and Control lens with respect to comfort and vision. The statistical power was calculated for different scenarios of sample sizes (N), SDs and inter-subject correlation (ρ). The results are summarized below:

Table 6: Power Analysis for CLUE scores

Sample Size (N)	Inter-subject correlation (ρ)	Power (%) $\sigma = 24$	Power (%) $\sigma = 26$
150	0.4	0.638	0.570
	0.5	0.717	0.648
	0.6	0.809	0.744
200	0.4	0.763	0.695
	0.5	0.834	0.772
	0.6	0.906	0.857
250	0.4	0.850	0.790
	0.5	0.907	0.857
	0.6	0.956	0.923

Under the assumption of no difference between Test and Control, the power analysis results showed that a sample size between 150 and 250 is considered sufficiently large to demonstrate the non-inferiority. The power analysis was conducted using the PROC POWER procedure available in SAS for paired tests.

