Study Endpoints	
Co-primary endpoint(s):
 
 • Overall comfort after 1-week of lens wear • Overall quality of vision after 1-week of lens wear 
Secondary endpoint(s):
 
 • Average daily wear time (in hour) • Monocular distance visual performance 
Additional Endpoints:
 
 • Slit lamp findings • Subject reported ocular symptoms • Lens fitting characteristics • Lens wettability • Adverse events
Study Design	
This study is a multi-site, group sequential, adaptive, randomized, double-masked, 2×2 crossover design, 1-week dispensing study. Subjects will wear bilaterally both Test and Control lenses in a random order for 1-week each as a daily disposable modality with a wash-out period of 1 week between the wearing periods.
 
See the flow chart at the end of the synopsis table for the schematic of the study visits and procedures of main observations (Figure 1).

Sample Size	In Phase 1, up to 160 eligible subjects will be enrolled and randomized into the study to ensure that approximately 150 subjects complete as cohort. An interim analysis will dictate if additional subjects will be enrolled in Phase 2 up to a maximum of 260.
Study Duration	For Phase 1, the study will last approximately 3 months and include an enrollment period of 3 weeks.
Anticipated Study Population	Healthy male and female volunteers (at least 18 and not more than 70 years old) who are habitual wearers of daily disposable contact lenses (approximately 80% 1-Day ACUVUE Moist, approximately 20% other daily disposable hydrogel contact lens brands) and have a spectacle astigmatism of $\leq 0.75\text{D}$ in both eyes.

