3. TARGETED STUDY POPULATION

3.1. General Characteristics

The population to be studied will be healthy male and female volunteers (at least 18 and not more than 70 years old) who are habitual wearers of daily disposable (approximately 80% 1 Day ACUVUE MOIST, approximately 20% any other brand of hydrogel daily disposable contact lens) and have a spectacle astigmatism of <0.75 D in both eyes. Up to 250 subjects will be enrolled to ensure approximately 240 subjects successfully complete the study.

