4. STUDY DESIGN AND RATIONALE

4.1. Description of Study Design

This study is a multi-site, group sequential, adaptive, randomized, double-masked, 2×2 crossover design, 1-week dispensing study. Subjects will wear bilaterally both Test and Control lenses in a random order for 1-week each as a daily disposable modality with a wash-out period of 1 week between the wearing periods.

Period 1:

At study Visit 1, subjects will be consented and screened for inclusion/exclusion criteria. If a subject is found to meet all eligibility criteria (see Section 34.), they will be randomly assigned to either Test/Control or Control/Test sequence using 1:1 ratio (i.e. 1/2 of subjects on the Test/Control sequence and 1/2 on the Control/Test sequence). Subjects will fit the first pair of lens in both eyes based on the sequence assigned; otherwise, the subject will be deemed ineligible for this study. Subjects will be advised to wear the study lenses at least 8 hours a day for a minimum of 6 days.

Successfully dispensed subjects at the Visit 1 will be scheduled for a follow-up visit (Visit 2). The follow-up visit will occur approximately 7 ± 2 days after the Visit 1. Unscheduled follow-up visits may occur during the study. At this visit, CLUE comfort and vision, slit lamp findings will be captured.

Wash-out period:

After completion of Visit 2, there is a 7 to 9 day washout period during which subjects may use their habitual products.

Period 2:

Following the washout period, the subject returns for Visit 3 and post-washout baseline evaluation will take place prior to lens fitting. After baseline evaluation, subject will be fitted and dispensed with the second pair of lens in the assigned sequence. Subjects will be advised to wear the study lenses at least 8 hours a day for a minimum of 6 days.

Visit 4 takes place 7 ± 2 days after Visit 3, at which CLUE comfort and vision, slit lamp findings, final evaluation will take place.

Both study lenses will be worn as a daily disposable modality. JJVC will provide the investigational sites with sufficient quantities of study lenses and supplies to complete the study.

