4.3. Enrollment Target and Study Duration

This is a group sequential, adaptive design where the enrollment will be performed in two phases. In the first phase, up to 160 subjects will be initially enrolled and approximately 150 are targeted to complete the study. An interim analysis will be performed when all subjects have completed Phase 1. The interim analysis will be used to estimate if more subjects are needed. If needed, additional subjects will be added to the study, in phase 2, up to a maximum of 260.

The population to be studied will be healthy male and female volunteers (at least 18 and not more than 70 years old) who are habitual wearers of daily disposable (approximately 80% 1 Day ACUVUE MOIST, approximately 20% any other brand of hydrogel daily disposable contact lens) and have a spectacle astigmatism of <0.75 D in both eyes. Up to 165 subjects will be enrolled to ensure approximately 150 subjects successfully complete the study.

There will be a total of 4 visits and the study duration for Phase 1 will be approximately 3 months:

- Visit 1:** (Day 0): Baseline Screening and Initial Randomization/Dispensing Visit Treatment #1
- Visit 2:** (Day 5-9): 1-Week Follow-Up Visit with first pair of study lenses/Dispensing Visit Treatment #2
- Visit 3:** (Approximately 1 Week from Visit 2): Post wash-out baseline and Dispensing Visit for Treatment #2
- Visit 4:** (Day 5-9 from Visit 3): 1-Week Follow-up Visit with second pair of study lenses and study exit

The Investigator is responsible for ensuring that all subjects entering the study conform to subject selection criteria. The number of subjects targeted for randomization and completion are as follows:

Table 1: Target number of subjects by arm and phase

	Phase 1		Phase 2		All
	Test/Control	Control/Test	Test/Control	Control/Test	Total
Randomization	80	80	50	50	260
Completion	75	75	45	45	250
Number of sites					
Subjects/site (Min-Max)					

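### Table 1's completion targets add to 240 but its printed total is 250, and the protocol states the maximum sample size, enrolment caps and replacement rule inconsistently; the effect on power is small

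*Combined protocol and SAP*

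**What the plan says.** The protocol states the size of the trial in several places:

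- **Sections 4.2 and 14.2:** the adaptive design runs "with a maximum of 250 evaluable subjects and a minimum of 150 subjects".
- **Section 4.3, Table 1:** by phase and sequence, with the overall total last, the rows read "Randomization 80 80 50 50 260" and "Completion 75 75 45 45 250".
- **Synopsis:** "An interim analysis will dictate if additional subjects will be enrolled in Phase 2 up to a maximum of 260". Sections 4.3 and 14.2 give the same cap of 260.
- **Section 3.1:** "Up to 250 subjects will be enrolled to ensure approximately 240 subjects successfully complete the study".
- **Section 4.3, first paragraph (Phase 1):** "up to 160 subjects will be initially enrolled and approximately 150 are targeted to complete the study".
- **Section 4.3, second paragraph:** "Up to 165 subjects will be enrolled to ensure approximately 150 subjects successfully complete the study". This sentence does not name a phase; the figure of 150 points to Phase 1.

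On replacement, Section 5.2 says that discontinued subjects are not replaced, while Section 8.2 says that an additional subject is enrolled when one discontinues early. Neither says whether replacements count within the 260. The term evaluable is not defined; Section 14.3 defines only the safety, per-protocol and ITT populations.

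**The concern.** The completion row of Table 1 does not add up, and the randomisation row beside it does. Both rows carry five values under the same headings, so a fault in the text extraction is an unlikely explanation. The number 250 is also used in two senses: as an enrolment cap in Section 3.1, and as a count of evaluable subjects in Sections 4.2 and 14.2. A reader cannot tell how many completers the final analysis is planned on, or how many subjects may be randomised to reach them.

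This matters more than usual because the design is adaptive. Section 14.8 decides whether to recruit Phase 2 from a predictive probability, which has to be computed against some final sample size. Sections 14.1, 14.4 and 14.8 leave the details and operating characteristics to a stand-alone SAP, to be finalised before the interim. If the protocol supports two maxima at that point, the choice between them would be hard to defend once interim results have been seen.

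**Working it through.** **Table 1 by addition**

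- Randomisation: 80 + 80 + 50 + 50 = 260, as printed.
- Completion: 75 + 75 + 45 + 45 = 240; printed 250.

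**Completion rates implied by each statement**

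| Source | Completing / enrolled | Rate |
|---|---|---|
| Phase 1 (synopsis, 4.3, 14.2, Table 1) | 150/160 | 93.75% |
| 4.3, second paragraph | 150/165 | 90.9% |
| Table 1, Phase 2 cells | 90/100 | 90% |
| Table 1, sum of cells | 240/260 | 92.3% |
| Table 1, printed totals | 250/260 | 96.2% |
| 3.1 | 240/250 | 96% |

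**Completers from 260 randomised**, taking evaluable to mean completer and no replacements beyond the cap:

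- Table 1's own cells: 150 + 90 = 240.
- Phase 1 at 150, Phase 2 at the Phase 1 rate: 150 + 100 × 0.9375 = 243.75, about 244.
- 165 enrolled in Phase 1 with 150 completing: 260 − 165 = 95 places remain, so at most 150 + 95 = 245.
- Section 3.1's 96% applied throughout: 260 × 0.96 = 249.6, about 250.

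**Power.** Inputs from Sections 2.3 and 14.2: margin 5 CLUE points, true difference 0, σ = 24 or 26, ρ = 0.4, 0.5 or 0.6, paired test. The protocol does not state sidedness; one-sided 0.025 is what reproduces Table 6.

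- SD of the difference = σ√(2(1 − ρ))
- Noncentrality = 5√N / SD of the difference, with N − 1 degrees of freedom
- Power = probability that the noncentral t exceeds the central t critical value at one-sided 0.025

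This reproduces all 18 cells of Table 6 to within 0.0005. One-sided 0.05 does not: it gives 0.912 where the table prints 0.850 (N = 250, ρ = 0.4, σ = 24).

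Example with σ = 24, ρ = 0.5: the SD of the difference is 24 × √1 = 24. At N = 250 the noncentrality is 5 × 15.81/24 = 3.29 and power is 0.907. At N = 240 it is 5 × 15.49/24 = 3.23 and power is 0.895.

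| ρ | N = 250, as printed (σ 24 / 26) | N = 240 (σ 24 / 26) | Loss in points |
|---|---|---|---|
| 0.4 | 0.850 / 0.790 | 0.835 / 0.773 | 1.5 / 1.7 |
| 0.5 | 0.907 / 0.857 | 0.895 / 0.843 | 1.2 / 1.4 |
| 0.6 | 0.956 / 0.923 | 0.949 / 0.913 | 0.7 / 1.0 |

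At N = 244 the loss is 0.4 to 1.0 points. All of these are for a single endpoint at a fixed N. They allow neither for the co-primary requirement nor for the interim look.

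**The case against.** The strongest defence is that only one printed number is arithmetically wrong. The sentence in Sections 4.2 and 14.2 sets a ceiling, and an expected 240 under a ceiling of 250 is no contradiction. Table 6 is a grid of scenarios, correct as printed, and Section 14.2 concludes only that a size between 150 and 250 is sufficient; 240 lies within that range. All of this stands, and it rules out several stronger readings that a reader might infer:

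- **That Table 6 is wrong or the trial is underpowered.** The table reproduces exactly, and no target power is stated that 240 would miss.
- **That 250 completers cannot be reached within 260.** This holds only if Phase 1 yields exactly 150 completers, which would leave no room for Phase 2 dropout. The protocol says approximately 150, and Section 3.1's own 96% gives about 250 from 260. Replacements outside the cap, or counting ITT subjects with partial data as evaluable, would also reach it.
- **That 240 is plainly the intended number.** Section 3.1 and Table 1's cells point to 240; Sections 4.2 and 14.2, Table 6's top row and the printed total point to 250.
- **That the predictive probability is miscalculated.** Section 14.8 gives no N for it. The link is a reason to settle N, not a demonstrated error.

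The replacement conflict is also less certain than the table error. The sentence in Section 5.2 closes a paragraph on unmasking and follows one on unmasked subjects, so a narrower scope is possible, although its wording is general.

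The defence does not remove the wrong total, the two meanings of 250, or the 160 and 165 within one section.

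**Conclusion.** The point holds as an error in stated numbers and a lack of consistency, and it should be corrected. Table 1's completion total is wrong against its own cells by 10 subjects. The maximum, the Phase 1 cap and the replacement rule are not stated consistently. The finding does not overturn the design: even if the final analysis has 240 rather than 250, power falls by 0.7 to 1.7 points in the Table 6 scenarios.

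The table sum needs no assumption. The power comparison rests on Table 6's own inputs, on evaluable meaning completer, and on no replacements beyond 260. Which of 240 and 250 is intended is for the sponsor to say.

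**What to change.** 1. State one intended maximum number of completers and one enrolment cap. Make Table 1's cells and total and Sections 3.1, 4.2, 4.3 and 14.2 agree with them, settle 160 or 165 for Phase 1, and define evaluable.
2. If 240 is intended, correct Table 1's total. Table 6 can stay as it is, with a row added at N = 240 (σ 24/26: 0.835/0.773 at ρ = 0.4, 0.895/0.843 at 0.5, 0.949/0.913 at 0.6).
3. If 250 is intended, change the Phase 2 completion cells and justify the completion rate they need within the cap: 250/260 = 96.2% overall, against the 90% that the Phase 2 cells now imply. If that rate is not credible, the cap has to rise.
4. Reconcile Sections 5.2 and 8.2 to one replacement rule and say whether replacements count within the 260.
5. Use the same N for the predictive probability in the SAP, fixed before the interim analysis.

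With 240 completers this costs only edits to the text and one table, with no extra subjects. Keeping 250 costs a more demanding retention assumption or additional randomised subjects.

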2.3. Hypotheses

Primary Hypotheses:

There are two co-primary hypotheses in this study. Both of them must be met to satisfy the primary objective of the study.

1. The Test lens will be non-inferior to the Control lens with respect to overall CLUE comfort score at the follow-up visit. A non-inferiority margin of -5 points will be used.
2. The Test lens will be non-inferior to the Control lens with respect to overall CLUE vision score at the follow-up visit. A non-inferiority margin of -5 points will be used.

Secondary Hypotheses:

1. The Test lens will be non-inferior to the Control lens with respect to average daily wear time at 1-week follow-up visit. A non-inferiority margin of 1 hour will be used.

2. The Test lens will be non-inferior to the Control lens with respect to logMAR visual performance (using ETDRS visual acuity charts) at the follow-up visit. A non-inferiority margin of 0.05 logMAR will be used.

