14.4. Level of Statistical Significance

All planned analysis for this study will be conducted with an overall type I error rate of 5%. Type I error will be controlled for multiplicity across interim analysis and final analysis. The operating characteristics of this adaptive trial will be provided in the SAP.

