14.5. Primary Analysis

The co-primary endpoints for this study are the CLUE comfort and the CLUE vision scores evaluated after 1-week of lens wear. The primary analysis will be conducted on per-protocol and ITT populations. Both primary hypotheses must be met to meet the primary objective of the study.

CLUE Comfort and Vision scores

CLUE comfort and vision scores will be analyzed separately using a Bayesian repeated measurement random-effects model to compare between Test and Control lenses. Each regression model will include baseline values, lens type, lens wearing sequence and lens wearing period as fixed effects and investigational site as random effect. Other subject characteristics such as age, gender and will also be included as fixed effects when appropriate. Unstructured covariance matrix will be used to model the residual errors among observations within subjects. Non-informative prior distributions will be used for the coefficients in the models as well as for the error terms. Independent vague normal $N(0,1000)$ priors will be used for the regression coefficients, inverse gamma $IG(0.001, 0.001)$ for the variance of the random effect site and inverse Wishart for the residual errors. The Metropolis sampler algorithm as implemented in the SAS MCMC Procedure will be used to carry out parameter estimation. Results will be reported as regression coefficient mean estimates with credible intervals.

The null and alternative hypotheses for non-inferiority of Test lens relative to Control are as follows:

$$H_0: \Delta < -5$$
$$H_A: \Delta \geq -5$$

where Δ is the CLUE score mean difference between Test lens and Control lens (Test minus Control). Non-inferiority will be declared if the lower bound of the credible interval of the mean difference between Test and Control is greater than -5. Superiority will be declared if the lower bound of the credible interval of the mean difference between Test and Control is greater than 0. The superiority test will be performed only if non-inferiority is established.

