14.8. Interim Analysis

This is a group sequential adaptive trial with stopping rules for non-inferiority and superiority. The study will be conducted in two phases. In Phase 1, up to 160 subjects will be enrolled with a target completion of 150. The data from Phase 1 will then be analyzed to see if non-inferiority/superiority can be concluded. The following stopping rules will be considered:

- If non-inferiority can be concluded, test for superiority. If superiority can be concluded stop the study for early success. Otherwise, calculate the predictive probability (PP) of superiority. If $PP < 0.20$, stop the study. If $PP \geq 0.80$, continue the trial and recruit the Phase 2.
- If non-inferiority can't be concluded. Calculate the PP of non-inferiority. If $PP < 0.20$, stop the study. If $PP \geq 0.80$, continue the trial and recruit the Phase 2.

More details will be provided in the SAP.

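### Table 6 gives the power for one CLUE endpoint at one fixed look, but the primary objective requires both comfort and vision, so it overstates the chance of meeting that objective.

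*Combined protocol and SAP*

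**What the plan says.** Section 2.3 sets out two co-primary non-inferiority hypotheses, CLUE comfort and CLUE vision, and says of each that "A non-inferiority margin of -5 points will be used". On the success rule it says "Both of them must be met to satisfy the primary objective of the study", and section 14.5 repeats this: "Both primary hypotheses must be met to meet the primary objective of the study".

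Section 14.2 assumes no true difference between the lenses on either score. Table 6 then gives one power value for each combination of N (150, 200, 250), correlation ρ (0.4, 0.5, 0.6) and SD (24, 26). On method it says "The power analysis was conducted using the PROC POWER procedure available in SAS for paired tests". It concludes that "the power analysis results showed that a sample size between 150 and 250 is considered sufficiently large to demonstrate the non-inferiority".

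Section 14.8 adds an interim analysis: "This is a group sequential adaptive trial with stopping rules for non-inferiority and superiority". Section 14.4 requires type I error control across the interim and final analyses and says "The operating characteristics of this adaptive trial will be provided in the SAP". Section 14.2 gives no joint power for the two endpoints, no comfort–vision correlation and no allowance for the interim look.

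**The concern.** A reader of section 14.2 will take the Table 6 values, in particular 0.850, 0.907 and 0.956 at the maximum N, as the chance of meeting the primary objective. Nothing in the table says they are per endpoint. If they are, they answer an easier question than the trial asks, because the trial succeeds only when comfort and vision both pass. The statement that 150 to 250 subjects are enough would then rest on power for the wrong event. Type I error is not affected, since requiring both endpoints needs no alpha split. What is at stake is whether the sponsor knows how likely the trial is to succeed.

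**Working it through.** **Inputs.** Margin 5 (section 2.3). True difference 0, SD 24 or 26, ρ = 0.4, 0.5 or 0.6, and N = 150, 200 or 250 (section 14.2). Pooled historical SDs are 23.93 for comfort and 21.67 for vision (Table 5). The comfort–vision correlation r, between the two test statistics, is not in the documents and is assumed to run from 0 to 0.7.

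**Step 1: reproduce Table 6.** For one endpoint, SD of the paired difference = σ√(2(1−ρ)) and noncentrality = 5√N / SD of the difference. Power is the probability that a noncentral t with N−1 degrees of freedom exceeds the one-sided 0.025 critical value. For σ = 24, ρ = 0.5, N = 250:

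- SD of the difference = 24 × √1 = 24
- noncentrality = 5 × 15.811 / 24 = 3.294
- critical value 1.970, power 0.907, as printed.

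All 18 cells match to three decimals. One-sided 0.05 does not reproduce the table: at N = 150, ρ = 0.5, σ = 24 it gives 0.815 against the printed 0.717. So each cell is the power of one test on one endpoint at one look.

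**Step 2: direction.** P(comfort and vision both pass) ≤ P(comfort passes), and it is strictly lower for r below 1. No assumed value is needed for this.

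**Step 3: size at a single look.** Take SD 24 for comfort and 22 for vision, the Table 5 totals rounded to whole points. Joint power is the bivariate normal probability at the probits of the two single-endpoint powers, with correlation r. For N = 250, ρ = 0.5, vision alone has noncentrality 5 × 15.811 / 22 = 3.593 and power 0.947. At r = 0 the joint value is 0.907 × 0.947 = 0.859; at r = 0.7 it is 0.883.

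| N | ρ | Printed, σ = 24 | Both endpoints, r = 0 to 0.7 |
|---|---|---|---|
| 150 | 0.4 | 0.638 | 0.46–0.56 |
| 150 | 0.5 | 0.717 | 0.57–0.65 |
| 150 | 0.6 | 0.809 | 0.71–0.76 |
| 200 | 0.4 | 0.763 | 0.64–0.71 |
| 200 | 0.5 | 0.834 | 0.75–0.79 |
| 200 | 0.6 | 0.906 | 0.86–0.88 |
| 250 | 0.4 | 0.850 | 0.77–0.81 |
| 250 | 0.5 | 0.907 | 0.86–0.88 |
| 250 | 0.6 | 0.956 | 0.94–0.95 |

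Simulated paired data (20,000 trials per cell, success when both lower limits exceed −5) agree: at N = 250, 0.767–0.809, 0.860–0.878 and 0.935–0.945. With SD 26 for comfort and 24 for vision at N = 250, joint power is 0.67–0.74, 0.78–0.82 and 0.88–0.90, against printed 0.790, 0.857 and 0.923.

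Using 24 for vision would be conservative. At SD 22, vision alone has power 0.714, 0.790 and 0.871 at N = 150. The shortfall therefore comes from the joint requirement, not from the choice of SDs.

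**Step 4: the whole two-look trial.** The documents give no boundaries, so this is illustrative. Looks are at 150 and 250 (information fraction 150/250 = 0.6), with one-sided 0.025 per endpoint. Boundaries are O'Brien–Fleming (2.572, 1.992) or Pocock (2.161, 2.161). Success requires both endpoints to cross at the same look. Predictive probability uses a flat prior. SDs are 24 and 22, r = 0 to 0.7, with 1,000,000 runs per scenario.

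| Rule after the interim | ρ = 0.4 | ρ = 0.5 | ρ = 0.6 |
|---|---|---|---|
| Stop if predictive probability < 0.20, otherwise continue | 0.65–0.77 | 0.76–0.85 | 0.88–0.92 |
| No futility stop | 0.71–0.80 | 0.82–0.88 | 0.91–0.94 |
| Printed, N = 250, σ = 24 | 0.850 | 0.907 | 0.956 |

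Section 14.8 gives no action when the predictive probability lies between 0.20 and 0.80, where about 23–45% of these simulated trials fall. If those trials stopped, the figures would be 0.36–0.50, 0.47–0.60 and 0.62–0.72.

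**The case against.** Four points can fairly be made for the plan.

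1. *The decision level is not stated.* Section 14.4 says 5% overall and section 14.5 gives no credible-interval level. At one-sided 5%, single-look joint power at N = 250 (SD 24/22) would be 0.865–0.888, 0.925–0.936 and 0.970–0.973, above the printed values. This is true, and the joint figures should carry their alpha. But Table 6 itself uses 0.025. At one-sided 5% the single-endpoint power would rise as well (0.912, 0.950 and 0.979 for comfort), so the like-for-like gap remains. Alpha control over two looks would also lower the joint figures.

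2. *The σ = 26 column is already cautious.* It exceeds both pooled SDs, and joint power at SD 24/22 with N = 250 lies close to it (0.790, 0.857, 0.923). A reader who used only that column would be little misled if the pooled SDs hold. That is an offset from a different SD assumption. It does not make the table joint power, and it disappears if the comfort SD really is 26.

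3. *The sentence gives a range of N.* Under the two main illustrative rules, whole-trial joint power lies between the printed N = 150 and N = 250 cells. This stands: the N = 150 rows are an interim look, and for the trial as a whole it is the N = 250 rows that overstate.

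4. *Operating characteristics are promised in the SAP.* The stand-alone SAP is not among the documents supplied, so joint power cannot be called missing from it. But section 14.2 draws its conclusion now, from Table 6 alone.

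Baseline adjustment in the model could also raise power, but neither the table nor the text claims that gain.

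**Conclusion.** The concern holds. Table 6 is arithmetically correct for what it computes, but that is not the power to meet the primary objective. At each fixed N, on the table's own alpha and the same comfort SD, the probability of meeting both co-primaries is lower than printed for any comfort–vision correlation below 1.

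The size depends on that undocumented correlation. For r from 0 to 0.7 and SD 24/22, the loss at N = 250 runs from about 1 point (0.956 − 0.946, ρ = 0.6) to 8 points (0.850 − 0.769, ρ = 0.4). The two-look figures rest further on assumed boundaries, the same-look success rule and the handling of the predictive probability, and should be read as illustration. The direction and the single-look sizes are firm on the stated inputs. This should be corrected, but it is a matter of reporting power correctly and not a flaw in the analysis.

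**What to change.** 1. Label Table 6 as power for one CLUE endpoint at fixed N: paired t test, margin 5, one-sided 0.025.
2. Add the probability of meeting both co-primaries at each fixed N, with separate comfort and vision SDs and a stated range of comfort–vision correlation.
3. Give the same probability over the two looks, using the credible-interval thresholds and predictive-probability actions actually adopted, either here or by cross-reference to the SAP.
4. Restate the conclusion, for example: *Assuming no true difference, SD 24 for comfort and 22 for vision, ρ from 0.4 to 0.6, a comfort–vision correlation from 0 to 0.7 and one-sided 0.025, the single-look probability of meeting both co-primary hypotheses is 0.46–0.76 with 150 completers and 0.77–0.95 with 250.*

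The cost is a short simulation and a few lines of text, and the stated power becomes less favourable. The enrolment limits, conduct and analysis do not need to change.
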